10.7.2. Proportion of subjects achieving renal response

Renal response is defined as (1) a decrease in proteinuria from baseline to Day 85 to a level of <300 mg/g creatinine and (2) maintaining the Day 85 estimated glomerular filtration rate (eGFR) within 15% of baseline. The number (%) of subjects achieving renal response will be calculated and presented. Subjects who discontinued prior to Week 12 will be counted as non-responders.

10.7.3. Proportion of subjects achieving partial renal response

Partial renal response is defined as (1) a decrease in proteinuria from baseline to Day 85 to a level of <1 g/g creatinine and (2) maintaining the estimated glomerular filtration rate (eGFR) within 15% of baseline. The number (%) of subjects achieving partial renal response will be calculated and presented. Subjects who discontinued prior to Week 12 will be counted as non-responders.

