Subjects who experience a decrease from baseline in eGFR $> 10 \text{ mL/min}/1.73 \text{ m}^2$ or $> 20\%$, (confirmed by repeat after 2 weeks) which is otherwise not explained (e.g., dehydration, new medication), or an increase in proteinuria of $> 3 \text{ g/g}$ creatinine from baseline or to a level $> 8 \text{ g/g}$ (confirmed by repeat after 2 weeks) during the 12-week treatment period, will exit the treatment phase of the study and be treated at the discretion of their primary nephrologist. They will remain in the study for follow up and outcome recording.

Subjects will be discharged from the study when all the Study Day 169 visit procedures have been completed. The subject's condition will be evaluated by the Investigator at the end of the clinical trial (Day 169) and appropriate standard of care medical treatment will be provided to all subjects as needed.

Number of Subjects

Up to approximately 20 male or female subjects with IgAN will be enrolled in this study. Subjects who started the CCX168 treatment period and drop out prematurely will not be replaced. However, subjects who drop out during the titration and run-in periods may be replaced.

Main Criteria for Inclusion

1. Biopsy-proven IgAN performed for clinical purposes within 3 years prior to screening;
2. eGFR $> 60 \text{ mL/min}/1.73 \text{ m}^2$ (by MDRD equation) OR eGFR $> 45 \text{ mL/min}/1.73 \text{ m}^2$ if eGFR has not declined $> 10 \text{ mL/min}/1.73 \text{ m}^2$ over the previous 24 weeks;

3. Proteinuria, defined as first morning urinary PCR > 1 g/g creatinine;
4. Male or female subjects, aged at least 18 years; Where allowed by local regulations, female subjects of childbearing potential may participate if adequate contraception is used during, and for at least the three months after study completion; Male subjects with partners of childbearing potential may participate in the study if they had a vasectomy at least 6 months prior to randomization or if adequate contraception is used during, and for at least the three months after study completion; Adequate contraception is defined as resulting in a failure rate of less than 1% per year (combined estrogen and progestogen [oral, intravaginal, or transdermal], or progestogen-only hormonal contraception (oral, injectable, or implantable), intra-uterine device, intra-uterine hormone releasing system, bilateral tubal occlusion, vasectomized partner, or sexual abstinence);

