5. Willing and able to give written Informed Consent and to comply with the requirements of the study protocol; and
6. Judged to be otherwise healthy by the Investigator, based on medical history, physical examination, and clinical laboratory assessments. Subjects with clinical laboratory values that are outside of normal limits (other than those specified in the Exclusion Criteria) and/or with other abnormal clinical findings that are judged by the Investigator not to be of clinical significance, may be entered into the study.

Main Criteria for Exclusion

1. Severe renal disease as determined by rapid decline in eGFR (defined as >10 mL/min/1.73 m² over 24 weeks prior to screening, not otherwise explained);
2. Pregnant or nursing;
3. Proteinuria > 8 g/day (or >8 g/g creatinine);
4. Patients with systemic manifestations of Henoch-Schönlein purpura within the last 2 years prior to screening;
5. Patients with IgAN deemed secondary to underlying disease: e.g., diabetes, liver disease, cirrhosis, celiac disease, HIV, inflammatory bowel disease, lymphoma, or associated with any other multi-system autoimmune disease;
6. Biopsy report demonstrating severe crescentic IgAN (>25% crescents), OR >50% interstitial fibrosis and/or tubular atrophy (“T2”) ([Cattran et al. 2009](#)), OR a high likelihood of rapid decline in eGFR based on an MEST (“Oxford”) classification (M = mesangial hypercellularity; E = endocapillary proliferation; S = segmental glomerulosclerosis/adhesion; T = tubular atrophy/interstitial fibrosis) score of M1, E0, T1, or M0/1, E1, T1 ([Cattran et al. 2009](#));
7. History of treatment with glucocorticoids, cyclophosphamide, azathioprine, mycophenolate mofetil, or any biologic immunomodulatory agent within the 24 weeks prior to screening;
8. Symptomatic congestive heart failure requiring prescription medication, clinically evident peripheral edema of cardiac origin, poorly-controlled hypertension (systolic blood

pressure >160 or diastolic blood pressure >95), history of unstable angina, myocardial infarction or stroke within 6 months prior to screening;

9. History or presence of any form of cancer within the 5 years prior to screening, with the exception of excised basal cell or squamous cell carcinoma of the skin, or cervical carcinoma *in situ* or breast carcinoma *in situ* that has been excised or resected completely and is without evidence of local recurrence or metastasis;
10. Positive HBV, HCV, or HIV viral screening test;

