After the 8-week run-in period has been completed, two back-to-back first morning urine collections need to be obtained for protein and creatinine measurements. The geometric mean of the two urinary PCR measurements must be > 1 g/g creatinine for eligibility for further study participation.

On Day 1, patients meeting inclusion criteria will start CCX168 treatment. Patients will take CCX168 30 mg orally twice daily for 12 weeks (84 days). The CCX168 dose will be taken in the morning optimally within one hour after breakfast and in the evening optimally within one hour after dinner. After the 84-day treatment period, patients will be followed for 12 weeks (84 days) while continuing to take their RAAS blocker treatment at a stable dose.

At post-Day 1 study visits, blood and urine samples will be collected for safety, efficacy, and pharmacokinetic measurements. A serum pregnancy test for women of childbearing potential will be done on Days 29, 43, 57, 85, 113, and 169. Physical examinations and vital signs assessments will be performed throughout the study. Concomitant medication and adverse event assessments will be made at every study visit. An optional renal biopsy could be performed after the 12-week treatment period to assess the effect of CCX168 treatment on kidney histology.

During the 12-week treatment period and the 12-week follow-up period, the dose(s) of RAAS blocker(s) must remain unchanged. No new RAAS blocker or non-dihydropyridine calcium channel blocker or diuretic may be added during the study period (active treatment period or follow up).

During the treatment period with study medication and the 12 weeks of follow up thereafter, no new immunomodulatory medication may be started including, but not limited to cyclosporine, tacrolimus, mycophenolate mofetil, azathioprine, cyclophosphamide, or glucocorticoids (e.g. prednisone).

Concomitant use of omega-3 fatty acid supplements (e.g., fish oil) is permitted IF the medication is started at the time of, or before screening, and is maintained at a stable dose during the rest of the study until the end of the follow-up period (Day 169).

Patients will visit the study center on Days 1, 8, 15, 29, 43, 57, 85, 113, 141, and 169 for the treatment and follow-up period.

Duration of treatment with study medicine: 84 days

Duration of follow up after end of treatment with study medicine: 84 days

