10.2.4. Definition of Baseline

For all analyses, baseline will be defined as the most recent measurement prior to the date and time of the first administration of CCX168. Baseline can be on the same day as the first dose of study medication, but prior to administration of study drug (typically the Day 1 pre-dose value). For urinary PCR, baseline will be the geometric mean (GM) of the two measurements made in the Day -7 to -2 window plus the Day 1 (pre-dose) value. For the eGFR, urinary ACR, MCP-1:creatinine ratio, EGF:MCP-1 ratio, and microscopic RBC count, baseline will be the geometric mean of the one measurement made in the Day -7 to -2 window plus the Day 1 (pre-dose) value.

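### Partial renal response uses the 1 g/g entry cut-off in a single arm with no reference rate, so an unknown part of the reported proportion is chance crossing

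*SAP*

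**What the plan says.** **Entry.** The inclusion criteria (Protocol 4.2) require "Proteinuria, defined as first morning urinary PCR > 1 g/g creatinine". After the run-in, Protocol 3 adds a second test: "The geometric mean of the two urinary PCR measurements must be > 1 g/g creatinine for eligibility". Protocol 6.3.3 repeats it with an upper limit of 8 g/g. The Day 1 sample is not part of either test.

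**Baseline.** SAP 10.2.4 uses three samples: "baseline will be the geometric mean (GM) of the two measurements made in the Day -7 to -2 window plus the Day 1 (pre-dose) value".

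**Response.** SAP 10.7.3 asks for "a decrease in proteinuria from baseline to Day 85 to a level of <1 g/g creatinine" and for "maintaining the estimated glomerular filtration rate (eGFR) within 15% of baseline". It adds: "Subjects who discontinued prior to Week 12 will be counted as non-responders". The Day 85 PCR is a single first-morning value, and any decrease from baseline is enough.

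**Reporting.** There is one treatment group (SAP 5.3). SAP 10.7.3 plans a number and percentage, and SAP 9.3 adds a confidence interval for efficacy percentages. Neither document states a null rate, a historical rate or a pre-treatment proportion to set beside it.

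**The concern.** When the selection line and the success line are the same, subjects whose usual PCR lies just above 1 g/g can be admitted on one set of samples and fall below the line on a later one with no change in disease. A concurrent control arm would show how often this happens. This trial has none, and the confidence interval describes precision around the observed rate without saying what rate to expect in the absence of a drug effect.

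There is also a smaller gap. Eligibility uses two samples and baseline uses three, so a subject can qualify, have a baseline already below 1 g/g, and count as a responder on a trivial further fall.

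At stake is the reading of a proportion that is easy to quote. In about 20 subjects, two to four partial responders could be taken as activity when chance might supply as many.

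**Working it through.** **No planned figure to reproduce.** The sample size section (Protocol 7.11, SAP 10.1) concerns the slope comparison only. Nothing is stated for partial response.

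**One subject.** Let the usual PCR be *m* and the within-subject log SD be *s*. The chance that a single value falls below 1 g/g is Φ(−ln *m* / *s*). With an assumed *s* = 0.3:

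- *m* = 1.2: Φ(−0.182/0.3) = Φ(−0.61) = 27%
- *m* = 1.5: Φ(−0.405/0.3) = Φ(−1.35) = 9%
- *m* = 2.0: Φ(−0.693/0.3) = Φ(−2.31) = 1%

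The overall rate therefore depends on how many subjects sit near the line, which the documents do not tell us.

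**A selected group, by simulation with no drug effect.** From the documents: screening PCR above 1 g/g; geometric mean of two run-in samples above 1 and at most 8 g/g; three-sample baseline; response if Day 85 is below 1 g/g and below baseline. Assumed: log-normal PCR, independent errors, no drift, and the values in the table.

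| Assumed inputs | Chance partial response |
|---|---|
| Median 1.2–2.0 g/g, between-subject log SD 0.4–0.6, within-subject CV 20–40% | 2.2% to 17.7% |
| Same, with within-subject log SD 0.2–0.4 | 2.3% to 18.3% |
| First row plus eGFR within 15%, eGFR CV 5% | 2.2% to 17.4% |
| First row plus eGFR within 15%, eGFR CV 8% | 1.9% to 15.4% |
| Median 1.2–3.0 g/g, CV 20–50%, no eGFR condition | 0.4% to 21.2% |

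The decrease-from-baseline condition removes at most 0.4 points. Full response (below 300 mg/g) is barely touched: a Day 85 value below 0.3 g/g arises by variation in at most 0.2%.

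**In 20 subjects.** 20 × 0.02 = 0.4 and 20 × 0.18 = 3.6 chance responders. By the binomial distribution, a 9% chance rate gives two or more in 55% of trials (1 − 0.91^20 − 20 × 0.09 × 0.91^19), and an 18% rate gives four or more in 50%.

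**Baseline already below the line.** Suppose the two run-in samples have a geometric mean of 1.05 and Day 1 is 0.80. Baseline is (1.05² × 0.80)^(1/3) = 0.96 g/g, and a Day 85 value of 0.95 meets the PCR criterion. With log SD 0.2–0.4, baseline is below 1 g/g in 0.4% to 4.5% of subjects. Such subjects contribute at most about 1.7 points of chance response.

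**Day 1 as a yardstick.** Day 1 plays no part in selection, so it carries the same regression toward the subject's usual level as Day 85. With no drift, the shares below 1 g/g at the two times agree within 0.3 points in every scenario (for example 12.3% and 12.2% at median 1.5 g/g, between-subject log SD 0.4, CV 40%). That agreement follows from the no-drift assumption. Adding a zero-mean drift of log SD 0.3 by Day 85:

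| Median, between/within log SD | Chance response at Day 85 | Day 1 below 1 g/g |
|---|---|---|
| 1.5, 0.4/0.3 | 13.8% | 9.0% |
| 2.0, 0.4/0.2 | 6.4% | 2.3% |

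**The case against.** The proportion does not stand in isolation. Besides the interval in SAP 9.3, the plan has PCR shift tables from baseline to each visit cut at 300 and 1000 mg/g (SAP 10.7.9), run-in PCR listings and summaries (SAP 10.6), geometric mean ratios with intervals (SAP 10.7.5) and individual PCR plots. The shift table will show who starts below 1 g/g. Response also needs stable eGFR, and early discontinuers count against it; both lower the chance rate. This is one of ten other efficacy endpoints in a pilot, with no test planned on it. All of this stands, and it limits the importance of the point. None of it supplies a rate to expect without drug.

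Three stronger readings are tempting and not supported:

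- *That the Day 1 pre-dose PCR is ignored.* It is one of the three baseline values and a point in both the run-in and treatment slopes (SAP 10.2.4, 10.7.1). It is unused only as a reference for this proportion.
- *That 2 to 18% is a property of this trial.* The documents contain none of the PCR inputs; the top of the range needs a median only just above the cut-off.
- *That Day 1 measures the full chance rate.* It falls 2 to 7 days after the qualifying samples, whereas Day 85 is 12 weeks into treatment. The drift example shows that it can understate chance crossing.

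The comparison must also be like with like. Setting a Day 85 composite that excludes baselines below 1 g/g against a PCR-only Day 1 share builds in a difference: in one no-effect scenario (median 1.2 g/g, log SDs 0.4/0.4), 16.6%, or 14.5% with the eGFR condition, against 18.6% at Day 1.

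**Conclusion.** The point holds as a low-cost improvement. It follows from the text alone that the entry and response cut-offs coincide, that no minimum fall is required, and that no reference rate is planned. The size does not: about 2 to 18% before the eGFR condition (top about 15 to 17% with it), and about 0 to 21% over wider inputs, all under assumed log-normal PCR with no drift. A low partial response rate, of the order of two to four in 20, is hard to interpret as the plan stands. The overlap of baseline with the response range is minor. A reader might infer that the efficacy conclusion is compromised; it is not, because the primary endpoint is the change in PCR slope and full response is hardly affected.

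**What to change.** 1. Keep partial renal response as the protocol defines it.
2. Beside it, for the same subjects (those with both values, with their number stated), report the proportion with PCR below 1 g/g at Day 1 pre-dose and at Day 85. Apply the PCR criterion alone at both times, with no eGFR condition and no baseline exclusion. Give the paired difference with an exact confidence interval.
3. State in a footnote that Day 1 reflects short-term variation only, that it is a minimum for the chance rate if PCR drifts over 12 weeks without a general upward trend, and that it is imprecise. With 20 subjects, 0/20 has an exact 95% interval of 0 to 17%, and 2/20 of about 1 to 32%.
4. Report how many partial responders had a baseline PCR already below 1 g/g, and give the proportion without them as a sensitivity result.

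The cost is a few table rows and a short addition to SAP 10.7.3. No new visit, sample or endpoint definition is needed.

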10.7.4. Change in slope from the run-in period to the treatment period for

- a. urinary ACR,
- b. eGFR,
- c. urinary MCP-1:creatinine,
- d. urinary EGF:MCP-1, and
- e. urinary microscopic RBC counts

These variables will be summarized similarly to the primary efficacy variable.

10.7.5. Percent change from baseline to Day 85 in

- a. urinary PCR and
- b. urinary ACR

Urinary PCR and ACR will be summarized with geometric mean, median, minimum, and maximum at each visit. Percent change from baseline will be based on the geometric mean ratios of Visit:Baseline. The 95% confidence interval for the geometric mean ratios will be presented.

10.7.6. Change from baseline to Day 85 in eGFR

Estimated GFR and its change from baseline will be summarized with arithmetic mean, standard deviation, SEM, median, minimum, and maximum at each visit. The 95% confidence interval for the change will be presented.

10.7.7. In patients with hematuria at baseline, the percent change from baseline in urinary RBC count

For the purpose of analysis, urinary RBC count will be recoded as follows. None = 0.1, Occ = 0.5, 1 - 2 = 1, 3 - 5 = 3, 6 - 9 = 6, 10 - 15 = 10, 16 - 29 = 16, 30 - 49 = 30, 50 - 75 = 50, >75 = 75.

The method of summary described in Section 10.6.5 applies here.

- 10.7.8. Percent change from baseline to Day 85 in urinary MCP-1:creatinine ratio;
Percent change from baseline to Day 85 in serum IgA:plasma C3 ratio ;
Percent change from baseline to Day 85 in urinary EGF:MCP-1 ratio

The method of summary described in Section 10.6.5 applies here.

- 10.7.9. Shift in Urinary PCR, ACR, and hematuria

Shift tables will be created for urinary parameters, such as urinary PCR, ACR, and red blood cells, from baseline to each visit. The categories of interest are <300 mg/g, 301-1000 mg/g, \geq 1000 mg/g for PCR and ACR, and \leq 5 RBCs/hpf, >5 to <30 RBCs/hpf, and \geq 30 RBCs/hpf for urinary RBC count.

- 10.7.10. Percent change from baseline in plasma and urinary biomarkers, e.g., C3a, C5a, properdin, and sC5b-9

If conducted, the results will be presented in a separate report.

10.8. Safety Analyses

Safety analyses will be conducted using the Safety Population.

10.8.1. Drug Exposure

Study drug compliance will be calculated for each patient by dividing the total number of capsules taken (number dispensed – number returned) by the total number prescribed. Duration of subject on CCX168 will be calculated as the time interval (weeks) between first and last dose of the study drug, inclusive. The total number of capsules prescribed is calculated as 6 capsules/day x number of days in the duration. The % compliance and duration of exposure will be summarized with descriptive statistics.

10.8.2. Adverse Events

Adverse events will be coded using MedDRA and displayed in tables using MedDRA SOC and PT.

Treatment emergent adverse event (TEAE) will be summarized using a subject incidence table. In the table, the number and percent (%) are calculated based on the number of unique subjects within each category (eg, PT). A subject reporting multiple events of the same category will be counted only once for the category. For summary purpose, AE relationship to the study drug will be grouped into "possibly related" or "probably not related". For subjects with more than one event coded to the same PT, the subjects will be counted for the categories with the strongest relationship and the greatest severity. On-treatment TEAEs and post-treatment TEAEs will be summarized separately.

An AE overview table summarizing the number (%) subjects meeting each of the following criteria will be presented, where appropriate.

- Treatment-emergent AE (TEAE)
- Possibly related TEAE
- TEAE leading to study drug discontinuation
- CTCAE Grade 3+ TEAE
- Treatment-emergent serious AE (TESAE)
- Related TESAE
- TEAEs with outcome of death

Additionally, the following subject incidence tables will be presented.

- TEAEs by PT sorted by the decreasing order of subject incidence
- TEAEs by SOC and PT sorted by the alphabetic order of the SOC and PT
- TEAEs by SOC and PT, grouped by relationship to study drug (possibly related or probably not related)
- TEAEs by SOC and PT, grouped by CTCAE grade

Data listings will be provided for subjects who died on study, experienced SAEs, or had AEs leading to study drug discontinuation.

A subject data listing will be provided for all adverse events. Included in the listing are the reported term, PT, SOC, TEAE flag, study day and study period (pre-treatment, on-treatment, and post-treatment) when AE starts, duration, relationship, severity, action taken, outcome, and seriousness category.

10.8.3. Laboratory Data

All laboratory reporting units will be converted to International System of Units (SI) units before any calculations. The actual value and change from baseline to scheduled post baseline visit will be summarized for hematology and chemistry. Additionally, subject incidences of shift from baseline classification (with respect to the normal range) to the post-baseline classification will be presented as a shift table. The summary and shift tables will be presented for all visits.

All laboratory data will be included in the by-subject and visit listings. Flags for laboratory values outside of normal limit (L and H) will be applied in the listings.

10.8.4. Vital Signs

Vital signs (body temperature, heart rate, respiration rate, systolic blood pressure, and diastolic blood pressure), and their changes from baseline will be summarized by visit. A subject data listing will be provided.

10.8.5. Physical examination

All physical examination findings will be presented in a data listing.

10.8.6. Concomitant Medications

Prior or concomitant medications will be coded using the WHODD. Subject incidences of the prior and concomitant medications will be tabulated by Anatomic Therapeutic Chemical classification (ATC3) and PT.

The use of concomitant medications will be included in a by-subject data listing.

The total daily dose of RAAS blockers at start of CCX168 dosing will be summarized by the Preferred Term.

11. CHANGES TO PLANNED ANALYSES

None.

APPENDIX A
List of Tables, Listings, and Figures

NUMBER	TITLE	POPULATION
Tables		
14.1.1.1	Disposition	MITT
14.1.1.2	Disposition	Safety
14.1.2.1	Subject Demographics	MITT
14.1.2.2	Subject Demographics	Safety
14.1.3	Baseline IgA Nephropathy Duration	Safety
14.1.4.1	Study Drug Exposure	MITT
14.1.4.2	Study Drug Exposure	Safety
14.1.5	Prior Medications by WHODD Anatomic Therapeutic Chemical Classification and Preferred Term	Safety
14.1.6	Concomitant Medications by WHODD Anatomic Therapeutic Chemical Classification and Preferred Term	Safety
14.2.1.1	Change from Baseline in Slope of Urinary Protein to Creatinine Ratio (PCR)	MITT
14.2.1.2	Change from Baseline in Slope of Urinary Protein to Creatinine Ratio (PCR)	PP
14.2.2.1	Subjects Achieving Renal Response	MITT
14.2.2.2	Subjects Achieving Renal Response	PP
14.2.3	Change from Baseline in Slope of Urinary Albumin to Creatinine Ration (ACR)	MITT
14.2.4	Change from Baseline in Slope of Urinary Estimated Glomerular Filtration Rate (eGFR)	MITT
14.2.5	Change from Baseline in Slope of Urinary MCP-1 to Creatinine Ratio	MITT
14.2.6	Change from Baseline in Slope of Urinary Epidermal Growth Factor (EGF) to MCP-1 Ratio	MITT
14.2.7	Change from Baseline in Slope of Urinary Microscopic Red Blood Cell (RBC) Counts	MITT
14.2.8	Percent Change from Baseline in Urinary Protein to Creatinine Ratio	MITT
14.2.9	Percent Change from Baseline in Urinary Albumin Creatinine Ratio	MITT
14.2.10	Percent Change from Baseline in Urinary RBC Count	MITT
14.2.11	Change from Baseline in eGFR	MITT
14.2.12	Percent Change from Baseline in Urinary MCP-1 to Creatinine Ratio	MITT
14.2.13	Percent Change from Baseline in Serum IgA to Plasma C3 Ratio	MITT
14.2.14	Percent Change from Baseline in Urinary EGF to MCP-1 Ratio	MITT
14.2.15	Shift in Urinary PCR from Baseline to Visit	MITT
14.2.16	Shift in Urinary ACR from Baseline to Visit	MITT
14.2.17	Shift in Urinary RBC from Baseline to Visit	MITT
14.3.1.1.1	Overall Summary of Treatment-Emergent Adverse Events	Safety
14.3.1.1.2	Overall Summary of Treatment-Emergent and Post Treatment Adverse Events	Safety
14.3.1.2.1	Treatment-Emergent Adverse Events by MedDRA Preferred Term in the Order of Decreasing Frequencies (Safety Population)	Safety
14.3.1.2.2	Treatment-Emergent and Post Treatment Adverse Events by MedDRA Preferred Term in the Order of Decreasing Frequencies (Safety Population)	Safety
14.3.1.3.1	Treatment-Emergent Adverse Events by MedDRA System Organ Class and Preferred Term in the Alphabetical Order (Safety Population)	Safety
14.3.1.3.2	Treatment-Emergent and Post Treatment Adverse Events by MedDRA System Organ Class and Preferred Term in the Alphabetical Order (Safety Population)	Safety
14.3.1.4.1	Treatment-Emergent Adverse Events by MedDRA System Organ Class and Preferred Term, Grouped by Relationship to Study Drug	Safety

14.3.1.4.2	Treatment-Emergent and Post Treatment Adverse Events by MedDRA System Organ Class and Preferred Term, Grouped by Relationship to Study Drug	Safety
14.3.1.5.1	Treatment-Emergent Adverse Events by MedDRA System Organ Class and Preferred Term, Grouped by the Worst Severity	Safety
14.3.1.5.2	Treatment-Emergent and Post Treatment Adverse Events by MedDRA System Organ Class and Preferred Term, Grouped by the Worst Severity	Safety
14.3.2.1a	Shift in Hematology Test Results from Baseline to Day 8	Safety
14.3.2.1b	Shift in Hematology Test Results from Baseline to Day 15	Safety
14.3.2.1c	Shift in Hematology Test Results from Baseline to Day 29	Safety
14.3.2.1d	Shift in Hematology Test Results from Baseline to Day 43	Safety
14.3.2.1e	Shift in Hematology Test Results from Baseline to Day 57	Safety
14.3.2.1f	Shift in Hematology Test Results from Baseline to Day 85	Safety
14.3.2.1g	Shift in Hematology Test Results from Baseline to Day 113	Safety
14.3.2.1h	Shift in Hematology Test Results from Baseline to Day 141	Safety
14.3.2.1i	Shift in Hematology Test Results from Baseline to Day 169	Safety
14.3.2.2a	Shift in Serum Chemistry Test Results from Baseline to Day 8	Safety
14.3.2.2b	Shift in Serum Chemistry Test Results from Baseline to Day 15	Safety
14.3.2.2c	Shift in Serum Chemistry Test Results from Baseline to Day 29	Safety
14.3.2.2d	Shift in Serum Chemistry Test Results from Baseline to Day 43	Safety
14.3.2.2e	Shift in Serum Chemistry Test Results from Baseline to Day 57	Safety
14.3.2.2f	Shift in Serum Chemistry Test Results from Baseline to Day 85	Safety
14.3.2.2g	Shift in Serum Chemistry Test Results from Baseline to Day 113	Safety
14.3.2.2h	Shift in Serum Chemistry Test Results from Baseline to Day 141	Safety
14.3.2.2i	Shift in Serum Chemistry Test Results from Baseline to Day 169	Safety
14.3.2.3a	Shift in Urinalysis Test Results from Baseline to Day 8	Safety
14.3.2.3b	Shift in Urinalysis Test Results from Baseline to Day 15	Safety
14.3.2.3c	Shift in Urinalysis Test Results from Baseline to Day 29	Safety
14.3.2.3d	Shift in Urinalysis Test Results from Baseline to Day 43	Safety
14.3.2.3e	Shift in Urinalysis Test Results from Baseline to Day 57	Safety
14.3.2.3f	Shift in Urinalysis Test Results from Baseline to Day 85	Safety
14.3.2.3g	Shift in Urinalysis Test Results from Baseline to Day 113	Safety
14.3.2.3h	Shift in Urinalysis Test Results from Baseline to Day 141	Safety
14.3.2.3i	Shift in Urinalysis Test Results from Baseline to Day 169	Safety
14.3.2.4a	Shift in Urine Chemistry Test Results from Baseline to Day 8	Safety
14.3.2.4b	Shift in Urine Chemistry Test Results from Baseline to Day 15	Safety
14.3.2.4c	Shift in Urine Chemistry Test Results from Baseline to Day 29	Safety
14.3.2.4d	Shift in Urine Chemistry Test Results from Baseline to Day 43	Safety
14.3.2.4e	Shift in Urine Chemistry Test Results from Baseline to Day 57	Safety
14.3.2.4f	Shift in Urine Chemistry Test Results from Baseline to Day 85	Safety
14.3.2.4g	Shift in Urine Chemistry Test Results from Baseline to Day 113	Safety
14.3.2.4h	Shift in Urine Chemistry Test Results from Baseline to Day 141	Safety
14.3.2.4i	Shift in Urine Chemistry Test Results from Baseline to Day 169	Safety
14.3.2.5	Summary of Hematology Test Results	Safety
14.3.2.6	Summary of Serum Chemistry Test Results	Safety
14.3.2.7	Summary of Urinalysis Test Results	Safety
14.3.2.8	Summary of Urine Chemistry Test Results	Safety
14.3.3	Summary of Vital Signs	Safety
Listings		
16.2.1.1	Subject Disposition	Safety
16.2.1.2	Subject Demographics	Safety
16.2.1.3	Screening Renal Biopsy	Safety
16.2.1.4	Medical History	Safety

16.2.1.5	Prior and Concomitant Medications	Safety
16.2.1.6	Study Drug Exposure	Safety
16.2.2.1	Urine Chemistry	Safety
16.2.2.2	Slope of Urinary Protein:Creatinine Ratio	Safety
16.2.2.3	Efficacy Parameters at Day 84 Compared to Baseline	Safety
16.2.2.4	Slope of Urinary Albumin:Creatinine Ratio	Safety
16.2.2.5	Slope of eGFR	Safety
16.2.2.6	Slope of Urinary MCP-1:Creatinine Ratio	Safety
16.2.2.7	Slope of Urinary EGF:MCP-1 Ratio	Safety
16.2.2.8	Slope of Urinary Microscopic RBC Counts	Safety
16.2.3.1	All Adverse Events	Safety
16.2.3.2.1	Laboratory Results: Hematology	Safety
16.2.3.2.2	Laboratory Results: Serum Chemistry	Safety
16.2.3.2.3	Laboratory Results: Urinalysis	Safety
16.2.3.3	Vital Signs	Safety
16.2.3.4	Physical Examinations	Safety
Figures		
1.1a	Spaghetti Plot of uPCR over Time Superimposed with Mean uPCR	MITT
1.1b	Spaghetti Plot of uPCR over Time Superimposed with Mean uPCR	PP
1.2a	Spaghetti Plot of uPCR over Time Superimposed with Regression Lines	MITT
1.2b	Spaghetti Plot of uPCR over Time Superimposed with Regression Lines	PP
2.1a	Bar Chart of Slopes During Week -8 to -5, -4 to -1, 1 to 4, and 1 to 12	MITT
2.1b	Bar Chart of Slopes During Week -8 to -5, -4 to -1, 1 to 4, and 1 to 12	PP
